Methods: Adult patients presenting for endoscopic closure of a gastrointestinal luminal defect will be enrolled and randomized 1:1 to closure of the defect with either the X-Tack system (the study group) or the Overstitch system (the control group.) Demographics, comorbidities, laboratory values, size of defect, time to close the defect, and the number of sutures to close the defect will be recorded. The primary outcome will be the time to closure of the defect. Secondary outcomes will include the rate of incomplete closures (as defined as either crossover to the other study group per endoscopist's discretion, or the need for additional modalities to close the defect such as endoscopic clips) as well as complications (bleeding, infection, perforation) and costs. Time to closure will be compared using the student T-test. To detect a 5-minute mean difference between the two groups at 80% power with an alpha of 0.05 and 1:1 randomization, 16 patients will be required in each group. Anticipating loss of subjects or data for technical or unanticipated reasons after randomization, we expect that 50 patients will need to be enrolled.

A. Specific Aims

The primary objective of the study is to compare the time required to close a defect or fistula in the gastrointestinal tract between the X-Tack system and the current standard of care (suturing with the Overstitch system.) The secondary objectives of the study will be to compare the rate of incomplete closures (as defined as either crossover to the other

study group per endoscopist's discretion, or the need for additional modalities to close the defect such as endoscopic clips) as well as complications (bleeding, infection, perforation) and costs between the X-Tack system and the current standard of care. We hypothesize that the X-Tack system will permit faster closure of endoscopic defects compared to the current standard, because the X-Tack does not require a different endoscope to use.

B. Background and Significance

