Perforation rates with endoscopic submucosal dissection (ESD) of colonic lesions and early cancers can be as high as 4% with delayed bleeding rates up to 8%. Endoscopic closure of resection defects has been shown to reduce delayed bleeding rates in the colon and is the least invasive method for closure of perforations or fistulas. Current options for closure include through-the-scope (TTS) clips, over-the-scope clips (OTSC,) and endoscopic suturing with the Overstitch system. TTS clips frequently misdeploy or are dislodged during complex closures and are cumbersome for the closure of large defects. OTSC are limited to closure of ~2 cm defects but are unable to capture the entirety of larger defects. The Overstitch system can close defects of any size but requires the use of a double-channel endoscope that is wide in diameter and is often too short to reach the right colon. It also requires removal of the endoscope that is being used for the resection from the patient in order to introduce the double-channel scope for closure. The X-Tack system offers the ability to close large defects with endoscopic sutures but can be introduced through the instrument channel of any standard endoscope, filling the gap between clips and suturing.

[figure not shown]
C. Preliminary Studies/Progress Report

The X-Tack is currently FDA cleared on the basis of similarity to previous suturing devices, though human data is pending. Preclinical animal data primarily compared the X-Tack to through-the-scope (TTS) clips. In the 24 X-Tack cases, 21 could be closed with just one X-Tack device, while a second device was used in 3 cases. Technical closure of defects in the animal model was successful in 24/24 cases using the X-Tack, versus just 13/16 cases using TTS clips. On necropsy, the time to complete healing of the defects was comparable between the X-Tack and TTS clip cases. On this basis, the investigators concluded that the X-Tack achieved expected levels of tissue healing and higher technical success rates than the current standard of care.

D. Research Design and Methods

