Time to closure will be compared using the student T-test. To detect a 5-minute mean difference between the two groups at 80% power with an alpha of 0.05 and 1:1 randomization, 16 patients will be required in each group (32 patients in total.) Anticipating loss to follow-up and patient dropout, we expect that a total of 50 patients will be required. Categorical variables will be compared using the chi squared test.

F. Gender/Minority/Pediatric Inclusion for Research

Women and minorities will be included in the research protocol.

G. Human Subjects

1. Provide number, age range, and health status of the subject population. List criteria for inclusion or exclusion.

We anticipate enrolling 50 patients in total.

Inclusion criteria: Patients > 18 years of age undergoing closure of a gastrointestinal luminal defect for which a suturing device would be otherwise indicated.

Exclusion criteria: INR > 2, platelets < 150, ongoing anticoagulation not meeting ASGE Antithrombotic Guidelines (Acosta RD et al, The Management of Antithrombotic Agents for Patients Undergoing GI Endoscopy, Gastrointest Endosc, 2016; 83(1): 3-16,) hemodynamic instability, ongoing or anticipated pregnancy

2. Identify sources of research material in the form of specimens, records or data.

Records and data will include chart data including demographics and comorbidities, laboratory values, endoscopy reports, and video acquired during endoscopy.

3. Describe plans for recruitment and consent procedures to be followed.

The endoscopist performing the procedure will meet the potential subject in the pre-procedure holding area. The endoscopist will review the consent documents with the potential subject. The subject will be provided time to review the entirety of the document and ask any questions of the endoscopist that they have. If they are amenable to proceeding, they will sign the consent and the procedure will be performed. No additional recruitment or inducement (i.e. advertising) is anticipated.

4. Describe risks and assess likelihood and seriousness.

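### Naming Welch's t-test instead of Student's for closure time is a cheap safeguard, needed only if spread and evaluable numbers both differ between arms

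*Combined protocol and SAP*

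**What the plan says.** The Methods summary and section E both name the test in the same words: "Time to closure will be compared using the student T-test". Neither place mentions unequal variances, an alternative test or the sidedness of the 0.05 level.

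The sample size is set "To detect a 5-minute mean difference between the two groups" "at 80% power with an alpha of 0.05 and 1:1 randomization", which gives 16 per group. No SD is stated, either common or by arm. Enrolment is raised from 32 to 50. The Methods summary explains this with the phrase "Anticipating loss of subjects or data for technical or unanticipated reasons after randomization"; section E attributes it to loss to follow-up and dropout. Neither gives a rate or a split by arm.

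The two workflows differ. Of the Overstitch system, section B says: "It also requires removal of the endoscope that is being used for the resection from the patient", so that a double-channel endoscope can be introduced. X-Tack passes through a standard endoscope. Section C reports that 3 of 24 animal closures with X-Tack used a second device. Section D allows crossover and additional clips in either arm.

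**The concern.** Pooling is sound when the two arms have the same spread, or when they have the same number of evaluable patients. The plan secures neither. Endoscope exchange, a second device, crossover and rescue clips could each lengthen some closures in one arm more than in the other. Losses after randomisation could leave unequal numbers.

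If both happen, the pooled standard error is wrong. It is too small when the smaller arm has the larger SD, and too large in the reverse case. The direction cannot be known in advance, and this is the trial's only primary p-value. Changing the test after seeing the variances or the losses would be a data-driven choice, so the time to settle it is now.

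**Working it through.** **1. The plan's own figure.** The formula is n per arm = 2 × (1.96 + 0.84)² × SD² / 5². With no SD stated, 16 cannot be reproduced from the documents. Solved backwards (two-sided), 16 per arm implies an SD of 4.89-5.04 min by the normal approximation, or 4.72-4.88 min by the exact t calculation. This is one common SD; nothing is implied about each arm separately. The allowance is 50 − 32 = 18 patients, or 18/50 = 36%.

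**2. Why both conditions are needed.** Compare the squared standard error that Student's test uses on average with the true one, for SDs s₁ and s₂:

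- Student: [(n₁−1)s₁² + (n₂−1)s₂²] / (n₁+n₂−2) × (1/n₁ + 1/n₂)
- True: s₁²/n₁ + s₂²/n₂

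Take SDs in the ratio 1:2 (assumed):

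- 16 v 16: Student (15 + 60)/30 × 0.125 = 0.3125; true 1/16 + 4/16 = 0.3125. They agree.
- 18 v 14, larger SD in the 14: Student (17 + 52)/30 × 0.1270 = 0.292; true 1/18 + 4/14 = 0.341. √(0.292/0.341) = 0.925, so the standard error is about 7% too small.
- 14 v 18, larger SD in the 18: Student (13 + 68)/30 × 0.1270 = 0.343; true 1/14 + 4/18 = 0.294. √(0.343/0.294) = 1.08, so it is about 8% too large.

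With equal SDs the two expressions coincide for any n₁ and n₂.

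**3. Type I error at nominal 5%.** Simulated normal data, 100,000 trials per case. The SD ratios are assumptions, because the plan gives no SDs.

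| Evaluable | SD ratio | Student, larger SD in smaller arm | Student, larger SD in larger arm | Welch |
|---|---|---|---|---|
| 16 v 16 or 25 v 25 | 1 to 2 | 5.0-5.4% (arms equal) | – | 4.9-5.1% |
| 14 v 18 | 1.5 | 6.2% | 4.2% | 4.9-5.0% |
| 14 v 18 | 2 | 7.1% | 3.8% | 5.0% |
| 20 v 25 | 2 | 6.9% | 3.7% | 4.9-5.0% |
| 16 v 25 | 2 | 9.0% | 2.6% | 4.9-5.1% |

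Unequal numbers with equal SDs give 4.9-5.1% for Student.

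**4. How likely the splits are.** Assume 25 per arm at randomisation and losses unrelated to arm.

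- 18 lost: the remaining 32 lie between 14/18 and 18/14 with probability 86%, and are at least as uneven as 20/12 with probability 4%.
- 16 v 25 means nine losses, all from one arm: 2 × C(25,9)/C(50,9) = 2 × 2,042,975 / 2,505,433,700 = 0.16%.
- 20 v 25 means five losses, all from one arm: 2 × C(25,5)/C(50,5) = 2 × 53,130 / 2,118,760 = 5.0%.

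**5. Cost of Welch in power.** Equal SDs of 4.88 min, 5-minute difference, 200,000 trials:

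| Evaluable | Student | Welch |
|---|---|---|
| 16 v 16 | 80.2% | 80.0% |
| 18 v 14 | 79.4% | 79.1% |
| 20 v 12 | 77.6% | 76.7% |
| 25 v 16 | 87.7% | 87.2% |
| 25 v 7 | 64.1% | 57.8% |

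When the SDs differ as well, the power gap mirrors the error gap. At 20 v 12 with ratio 2 and the larger SD in the 12, Student shows 80.4% against 68.2% for Welch, but at a type I error of 9.6%. With the larger SD in the 20, Welch is ahead, 83.5% against 74.0%.

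**6. Skewed times.** Lognormal data, assumed mean 15 min in both arms and SDs of 5 and 10. At 25 v 16 with the larger SD in the 16, Student gives 9.5% and Welch 7.0%. At 25 v 25 the figures are about 6.2% and 6.0%.

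**The case against.** The strongest reply is that unequal spread is assumed. No SDs are given, and the documented mechanisms pull in different directions: an endoscope exchange mainly shifts the mean in the Overstitch arm, while a second device would widen the X-Tack arm. The plan also does not say whether exchange time counts as closure time. All this stands, and it is why the result is given as a range in both directions.

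Allocation is 1:1, and closure time is recorded during the procedure, so missing the 48-72 hour telephone call does not remove the primary outcome. This also stands in large part. However, the Methods summary expects loss of subjects or data after randomisation, and technical losses could be related to the device. The documents do not quantify this.

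A reader might infer that the trial runs at about a 9% error rate. The documents do not support that: it takes an SD ratio of 2 together with a split that has 0.16% probability under arm-independent loss. Nor is 36% a stated loss rate; it is only the gap between 32 and 50.

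Because closure times cannot be negative and are probably right-skewed, a reader might also want a supportive analysis on log minutes. It is not recommended. It compares geometric means, which is a different null hypothesis. In simulations with equal mean minutes but unequal spread, it rejected 10-15% of the time, so it could contradict the primary result in the very situation at issue.

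**Conclusion.** The point holds as a low-severity, inexpensive improvement. Student's test rests on equal spread, which the plan neither states nor justifies, and nothing in the plan guarantees equal evaluable numbers. The realistic size is a type I error of about 6-7%, or about 4% in the reverse case, at 14 v 18 with an SD ratio of 1.5 to 2. With balanced arms it is about 5%.

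These figures assume normal data and SD ratios that the documents do not supply. The split probabilities assume 25 per arm and arm-independent loss; losses related to device could make the imbalance worse.

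It would go too far to say that the planned test is invalid or that Welch cures the problem entirely. A t-test on 1:1 arms is conventional and robust when the numbers are close. With strongly skewed times Welch reduces the drift but does not fully remove it. The missing SD, which leaves 16 per group unverifiable, is a separate and larger gap.

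**What to change.** In section E and in the Methods summary, replace the name of the test so that closure time is compared by:

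> Welch's unequal-variance t-test, two-sided, reporting the mean difference in minutes with 95% CI.

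This also settles the sidedness, which the plan leaves open. The endpoint, the estimate in minutes, the sample size and all procedures stay as they are.

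The cost is one sentence in two places and, if the SDs are in fact equal, 0-1 point of power at plausible splits. The loss is larger only at extreme imbalance: about 6 points at 25 v 7. No log-scale analysis needs to be added.

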Currently, the community standard is that gastroenterologists who are familiar with Overstitch start using the X-Tack without additional training. However, a hands-on demonstration session with the X-Tack device in a "dry lab" has been conducted with each endoscopist in the trial prior to the study in order to familiarize them with device before enrollment. Each endoscopist has also participated in a "wet lab" using an explant (porcine stomach) to simulate in vivo closure of defects using the X-Tack system. The device operates in a similar fashion compared to previous suturing devices, which are

used frequently by all endoscopists involved in this study. On this basis, all endoscopists in the study report comfort and familiarity with the X-Tack system, and the “break-in” period is not anticipated to affect safety or results during the study. The primary study visit will be comprised of the endoscopic procedure at the time of defect closure and a telephone call 48-72 hours later to assess for complications. Patient will be enrolled in the pre-procedure area. If the patient has a pre-procedure visit, they may be notified of their potential for enrollment in the study at that time, though not all patients have a pre-procedure visit in our practice. Patients will be randomized to closure with the X-Tack system versus closure with the Overstitch system prior to their procedure using a centralized computer-generated randomization. Technical success of closure, time of closure, number of sutures required, need for alternative modalities for closure, and any intraprocedural complications (bleeding, perforation) will be recorded. Any patient with possible periprocedural perforation will receive antibiotics at the endoscopist’s discretion. At the endoscopist’s discretion, the patient may cross over during the procedure to the other group if they believe that their current closure strategy is failing to safely close the defect. Alternate methods of closure (TTS clips, over-the-scope clips) may be used in either group if required by the endoscopist for safe closure of the defect. After the procedure, most patients are observed in the recovery area for 1-2 hours for any signs of complications before they are discharged home.

E. Statistical Methods

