Adverse events will be tracked and reported to the IRB at the time of interim analysis and final analysis (anticipated study time is less than one year.) Adverse events will be defined as bleeding, infection, or perforation occurring within 72 hours of the procedure. Severe adverse events will be reported to the IRB at the time of occurrence. Adverse events will be defined using the ASGE Adverse Event Lexicon (Cotton PB et al, A lexicon for endoscopic adverse events: report of an ASGE workshop. *Gastrointest Endosc*, 2010; 71(3): 446-454.) Severe adverse events in this lexicon are considered any adverse events resulting in hospital admission >10 days, ICU admission > 1 night, surgery for an adverse event or permanent disability. Severe adverse events will be reported using the OHR online portal.

b. adverse event (AE) grading

Adverse events will be graded according to the ASGE adverse event lexicon.

c. plan for unanticipated AE reporting

Severe adverse events will be reported to the IRB at the time of occurrence.

d. plan for annual reporting of AEs

The anticipated study time is less than one year, thus all reporting will occur at the time of interim analysis and final analysis.

e. interim efficacy analysis where appropriate

Perforation rate and complications related to inadequate closure (leak, fistula, peritonitis, bleeding) will be monitored. Perforation or complications related to inadequate closure > 50% compared to control group will lead to

stoppage of the trial. Interim analysis will be performed at the midpoint of enrollment (25 patients.) For instance, if after 25 patients have enrolled, 2 patients in the control group experience a complication, yet 4 experience a complication in the X-Tack group, the results will be reviewed with the independent safety monitor for possible stoppage of the trial pending discussion with the IRB.

2. If applicable, describe the Data and Safety Monitoring Board (DSMB) that will be responsible for monitoring the study.

An independent reviewer has been selected within the Jefferson Division of Gastroenterology who is outside of the investigator group who will review the interim analysis.

I. Literature Cited

2. Pohl H, et al. Clip Closure Prevents Bleeding After Endoscopic Resection of Large Colon Polyps in a Randomized Trial. *Gastroenterology* 2018;157:977-984.

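### Adverse events are defined to 72 hours, but the one scheduled follow-up call may be made at 48 hours, leaving up to 24 hours with no planned ascertainment

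*Combined protocol and SAP*

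**What the plan says.** Section H.1.a sets the events and the window: "Adverse events will be defined as bleeding, infection, or perforation occurring within 72 hours of the procedure". The Methods summary and Section A name the same three events as a secondary outcome.

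Section D describes how events are found:
- During the procedure, "any intraprocedural complications (bleeding, perforation) will be recorded".
- Afterwards, "most patients are observed in the recovery area for 1-2 hours" and then go home.
- The last scheduled step is "a telephone call 48-72 hours later to assess for complications".

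Section G.2 lists chart data as a source but names no adverse-event look-up and no date for one.

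On reporting, Section H.1.a says: "Adverse events will be tracked and reported to the IRB at the time of interim analysis and final analysis". It adds: "Severe adverse events will be reported to the IRB at the time of occurrence".

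Section H.1.e sets the interim look: "Interim analysis will be performed at the midpoint of enrollment (25 patients"). Its monitored events are perforation plus four complications attributed to poor closure: bleeding, leak, peritonitis and fistula. It gives no time window.

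**The concern.** An outcome defined over 72 hours needs a planned observation that reaches 72 hours. Here the call window ends where the event window ends, so a call made at any earlier permitted time stops short. A call can only collect what has already happened. A bleed, infection or perforation after an early call meets the definition, yet no scheduled step would find it.

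Two uses depend on the count: the secondary comparison of complications between arms, and the interim safety review. The independent reviewer can weigh only events that were captured. Section B itself refers to delayed bleeding, so the plan recognises that some relevant events occur after the procedure.

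The interim wording adds a smaller uncertainty. Its event list is not the adverse-event list, and nothing says whether that is deliberate or over what period its events count.

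**Working it through.** The plan gives no figure for completeness of follow-up, so there is none to reproduce. The check compares the windows, then the lists.

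**1. Event window against call window.** Inputs: the event window ends at 72 h (Section H.1.a); the call is made at time t, with t from 48 to 72 h (Section D). Time without scheduled ascertainment = 72 − t.

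| Call at | Gap | Share of the 72 h |
|---|---|---|
| 48 h | 72 − 48 = 24 h | 24/72 = 33% |
| 60 h | 72 − 60 = 12 h | 12/72 = 17% |
| 72 h | 0 h | 0% |

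If calls were spread evenly over the permitted range (an assumption), the average gap would be the 60 h row, 12 h. These are shares of time. The documents do not say what share of events falls between 48 and 72 h, so a number of missed events cannot be derived.

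**2. Other routes by which a late event could be found.**
- Recording during the procedure and recovery observation both end before the gap begins.
- Reporting of severe events at occurrence covers only the severe grade, which Section H.1.a describes by admission over 10 days, more than one night in intensive care, surgery or permanent disability. An event below that grade is outside this route.
- General tracking and chart data could pick up an event, but no procedure or time point is attached to them.

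**3. Interim count.** The interim look is tied to enrolment, and Section D says: "Patient will be enrolled in the pre-procedure area". Read literally, the 25th patient could contribute 0 of 72 h. Other windows still open = 50 × 3 days / accrual period. With even accrual of 50 patients (an assumption; the plan says only that the study should take less than one year):
- 12 months: 50 × 3/365 = 0.41
- 6 months: 50 × 3/182.5 = 0.82
- 3 months: 50 × 3/91.25 = 1.64

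So the 25th patient plus about 0.4 to 1.6 others would be affected, for at most about 3 days. This is small, but the same fix closes it.

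**4. Event lists.**

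| | Adverse events (H.1.a) | Interim rule (H.1.e) |
|---|---|---|
| In both | bleeding, perforation | bleeding, perforation |
| In one only | infection | leak, peritonitis, fistula |
| Window | 72 h | none stated |

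Some terms may overlap clinically, such as peritonitis with infection or leak with perforation, but no mapping is given. The lexicon that Section H.1.a also cites is not reproduced in the plan, so nothing here rests on it.

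**The case against.** The strongest reply is that late events would surface anyway: adverse events are tracked, severe ones are reported as they occur, and the chart is already a data source. This is fair and limits the likely loss. It does not remove the gap, because none of these is a scheduled check that reaches 72 h for every patient.

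A second reply is that a safety trigger may properly differ from an outcome. That stands. A reader might infer from the two lists that the interim and final analyses count different events. The documents do not support this as a finding: Section H.1.a has the 72 h events reported at both looks, and the secondary outcome names the same three events and so naturally takes the same window. What is missing is a sentence saying that the interim list is meant to differ, and over what period it applies.

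Three further inferences are tempting and should not be drawn:
- **That the 8% delayed-bleeding figure in Section B caps the loss.** 0.08 × 50 = 4 is an expected count at the upper quoted rate, not a bound. The rate is for colonic submucosal dissection and has no stated time window. The trial takes gastrointestinal defects generally and closes them, which Section B says lowers delayed bleeding in the colon.
- **That one missed event would reverse the interim trigger.** Section H.1.e illustrates with 4 against 2. At 3 against 2 the count ratio is 3/2 = 1.5, not above 1.5. Read as rates with an assumed 12 X-Tack and 13 control patients, it is (3/12)/(2/13) = 1.63, still above. The result depends on the reading.
- **That a baseline fistula which stays open would be miscounted.** Section H.1.e counts fistula only when related to poor closure, so this is conjecture.

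**Conclusion.** The mismatch is real and minor. A follow-up call that fully complies with Section D can leave up to 24 of the 72 hours in Section H.1.a with no scheduled ascertainment; a call at 72 hours leaves none. Complications can therefore be undercounted in the secondary outcome and in the interim safety review.

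This rests on the text alone: the 72 h definition, the 48 to 72 h call, and the absence of any dated adverse-event check on the chart. The number of events missed is unknown, and an estimate would need event rates and timings that the plan does not give. A reader might infer bias between X-Tack and Overstitch, but the call schedule is the same in both arms and nothing in the documents shows a difference. Time to closure is unaffected, and the sample size does not change.

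**What to change.** Keep the existing call and add a dated check of the chart data already collected, at or after 72 hours, for every patient. Alternatively, make the call at or after 72 hours with a stated upper limit. Close the interim count only once the chosen step is done for the 25th patient.

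In the same edit, reconcile the interim event list and its missing window with the adverse-event list in Section H.1.a, or state that the difference is intended. The choice of events and window is the sponsor's.

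The cost is protocol wording plus one chart check for each of 50 patients. A chart check sees only what that chart records. Moving the call instead avoids the extra check but gives up the earlier contact. Either way, the interim count closes about 3 days later. Reporting of severe events to the IRB at occurrence is unchanged.

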The primary potential risk of this research is device failure (i.e. failure to close defect or complications of closure, such as bleeding or perforation.) Device failure is expected to be uncommon. Most device failures are expected to be minor (i.e. perhaps requiring an additional device to complete closure of the rest of the defect, but no immediate harms or risks to the patient besides longer procedure time.) Serious complications (i.e. bleeding or perforation attributable to the device and requiring hospitalization) are expected to be very rare.

5. Describe procedures for protecting against or minimizing potential risks.

Because the research device will be used for defect closure during the same period of sedation as the current standard of care, participants should not perceive any difference in their procedure beyond signing an additional consent form. Patients with a propensity for bleeding i.e. thrombocytopenia or coagulopathy will be excluded to avoid adverse events.

6. Describe potential benefits and importance to the subjects and others.

Participants could potentially benefit from a faster defect closure with reduced anesthesia time. The ease of deployment of the X-Tack device also might make clinical success more likely. If the X-Tack device proves to be a faster, safer way to close mucosal defects or fistulas, future patients undergoing endoscopic submucosal dissection or fistula closure could benefit from less anesthesia time and a better chance at clinical and technical success.

7. Discuss why risks are reasonable in relation to benefits.

The risks and side effects of closure with the X-Tack system are anticipated to be identical to those of the Overstitch system. Given that the Overstitch is the current standard of care, and the X-Tack is anticipated to be faster and more user-friendly, the benefits of introducing the X-Tack outweigh the risks.

H. Data and Safety Monitoring Plan

1. Data and Safety Monitoring Plan (DSMP)

a. reporting mechanisms for adverse events to the IRB, FDA, and NIH.

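### Adverse events are defined in conflicting ways, the compared safety outcome leaves out sedation and other endoscope or device harms, and death is not expressly a trigger for prompt IRB reporting

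*Combined protocol and SAP*

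**What the plan says.** All references are to the combined protocol and SAP.

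- **Compared outcome.** The Methods abstract and Section A give the secondary safety outcome as complications and name three in brackets: bleeding, infection and perforation.
- **Recording during the procedure.** Section D names two intraprocedural complications to be recorded, bleeding and perforation. A telephone call at 48 to 72 hours then asks about complications.
- **Definition, H.1.a.** One sentence reads "Adverse events will be defined as bleeding, infection, or perforation occurring within 72 hours of the procedure". Two sentences later comes "Adverse events will be defined using the ASGE Adverse Event Lexicon".
- **Grading, H.1.b.** "Adverse events will be graded according to the ASGE adverse event lexicon". The lexicon's content is not reproduced, apart from a description of which events it regards as severe: "any adverse events resulting in hospital admission >10 days, ICU admission > 1 night, surgery for an adverse event or permanent disability".
- **Reporting, H.1.a and H.1.c.** "Adverse events will be tracked and reported to the IRB at the time of interim analysis and final analysis". The exception, stated in both subsections, is "Severe adverse events will be reported to the IRB at the time of occurrence".
- **Interim monitoring, H.1.e.** The list is perforation and complications of inadequate closure, given as leak, fistula, peritonitis and bleeding.
- **How the devices differ.** Section G.6 says "Participants could potentially benefit from a faster defect closure with reduced anesthesia time". Section B says the Overstitch system "requires the use of a double-channel endoscope that is wide in diameter", and that the resecting endoscope must be withdrawn to introduce it.

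**The concern.** The two H.1.a sentences can classify the same patient differently, and nothing says which one governs. If the closed list governs, a sedation-related aspiration is not an adverse event. It then cannot be a severe one, however long the ICU stay. If the lexicon governs, it may be both.

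Even if the lexicon governs Section H, it does not widen the outcome compared between arms or the recording list in Section D. The harms left out include those that could follow from the differences the plan describes: time under anesthesia, and passage of a second, wider endoscope. Section C also says that human data on X-Tack are pending, and a closed list is poorly suited to showing an unexpected device harm.

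The other matter at stake is prompt oversight. If the severe criteria are the only route to immediate reporting and do not name death, a literal reader of the protocol could hold a fatal event for a scheduled analysis.

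**Working it through.** The check is mainly textual. The plan has no figure on this point to reproduce.

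**Step 1. Set the lists side by side.**

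| Place | Bleeding | Infection | Perforation | Leak, fistula, peritonitis | Sedation or cardiopulmonary | Other endoscope or device injury |
|---|---|---|---|---|---|---|
| Methods abstract and A (compared outcome) | yes | yes | yes | no | no | no |
| D (recorded during procedure) | yes | no | yes | no | no | no |
| H.1.a, closed list, 72 hours | yes | yes | yes | no | no | no |
| H.1.a and H.1.b, lexicon | not shown | not shown | not shown | not shown | not shown | not shown |
| H.1.e (interim) | yes | no | yes | yes | no | no |

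No row names sedation or cardiopulmonary events, or injuries that neither bleed nor perforate. The only row that could include them rests on a source the plan does not reproduce. Death appears in no outcome, definition or reporting rule.

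**Step 2. Run hypothetical cases through the rules as written.**

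1. *Aspiration under sedation, more than one ICU night.* It is not in the compared outcome. Under the closed list it is not an adverse event and triggers nothing. If the lexicon governs and counts it, it is severe and is reported at occurrence. The two sentences of H.1.a can therefore give opposite instructions.
2. *Perforation from passing the wide endoscope.* It is counted in every named list, because none of them, apart from the closure-related part of H.1.e, is limited to events attributed to the closure device.
3. *Fatal bleed on day 1, no surgery, no more than one ICU night.* It is counted as bleeding in the arm comparison. It meets none of the four severe criteria: admission is not over 10 days, ICU stay is not over 1 night, there is no surgery, and permanent disability is not the same statement as death. Its report is deferred to the interim or final analysis.
4. *Fatal cardiopulmonary event on day 1, same course.* It is outside the compared outcome, outside the closed list, and meets none of the four criteria.

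**Step 3. Look for a safety net.** H.1.c, which covers unanticipated events, repeats the severe-only trigger. H.1.d places reporting at the interim and final analyses. Neither brings death in.

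**Step 4. Illustrate the size.** The plan gives no rate for sedation or other omitted events. The rates below are assumptions.

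- Expected patients affected = N × p, with N = 50 (Section E): 50 × 0.02 = 1.0; 50 × 0.05 = 2.5.
- Chance of at least one such patient = 1 − (1 − p)^50, assuming independence: 1 − 0.98^50 = 0.64; 1 − 0.95^50 = 0.92.

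At these rates at least one unlisted event is more likely than not, but one to three events across both arms are too few to compare. They can only be described.

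**The case against.** The strongest reply is that H.1.a does adopt a general lexicon, that H.1.b grades by it, and that the severe criteria are introduced as belonging to it. On that reading the three named types are the events of main interest, and broader harms are still captured. H.1.e also goes beyond the three types. This has weight: it would be wrong to say that the whole safety plan counts only bleeding, infection and perforation. That is accurate for the compared outcome. For Section H the defect is conflict between definitions.

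A reader might infer several stronger points that the documents do not support:

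- *That the top severity grade, or the grading scale, has no place for death.* No scale is printed. The plan describes what is severe, never says this is the highest grade, and leaves grading to the lexicon. Whether the lexicon has a separate fatal grade cannot be checked here.
- *That a fatal event escapes the arm comparison.* A fatal bleed, infection or perforation within 72 hours still counts. For those deaths only prompt reporting is in doubt.
- *That the trial is prevented from showing an expected safety advantage of X-Tack.* Section G.7 anticipates identical risks, and G.6 claims shorter anesthesia, not fewer anesthesia complications. A safer device appears there only as a possibility. Nor would the added events support a test.
- *That the illustrative counts can be set against the complications in the H.1.e example.* That example is hypothetical, concerns an interim look at 25 patients, and is not an expected event count.

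Institutional policy may require prompt reporting of any death. The protocol does not say so and should not depend on it.

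**Conclusion.** The point holds as one of inconsistent definitions and two gaps. The definitions in H.1.a conflict with each other and differ from the H.1.e list, the compared outcome and the Section D recording list. Following the narrower texts literally leaves sedation or cardiopulmonary events, and endoscope or device injuries without bleeding or perforation, unrecorded and uncompared. Death is not expressly a trigger for reporting at occurrence, so a rapid death meeting none of the four criteria would be deferred.

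The conclusion about definitions and death rests on the text alone. The size, 1.0 to 2.5 of 50 patients, rests wholly on the assumed 2% to 5% and is only an illustration. The primary outcome and the sample size are unaffected. The change should be made, because it is inexpensive and the gaps fall on harms related to differences between the devices that the plan itself describes.

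**What to change.** 1. Adopt one adverse event definition and use it in the Methods abstract, Section A, Section D and all of H.1, including the interim list in H.1.e. Amending H.1.a alone would leave the other lists in conflict.
2. Record and grade all adverse events in both arms. Name sedation or cardiopulmonary events and endoscope- or device-related events directly, so that the plan does not rely on what the lexicon may contain. Keep bleeding, infection and perforation as the named secondary outcome.
3. Tabulate all events by arm, descriptively, beside the three-type outcome.
4. Add death from any cause to the events reported to the IRB at occurrence, in both H.1.a and H.1.c.

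Possible text for H.1.a: *Every adverse event will be recorded and graded in both arms, including sedation, cardiopulmonary, endoscope-related and device-related events. Bleeding, infection and perforation are the components of the secondary safety outcome; all other events will be tabulated by arm without formal testing. Death from any cause and every severe adverse event will be reported to the IRB when they occur.*

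The cost is a few sentences of protocol text and some check boxes on the procedure form and the telephone script. The downside is slightly more events to record and grade, some of them unrelated to closure.
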